9.3.3. Pathway Enrichment Analysis

Pathway enrichment analysis will be carried out separately for each DE gene set identified (post vs. pre-vaccination as well as between study arm comparisons) using published pathway information obtained from KEGG [13] (KEGG Pathways), MSigDB [14] (MSigDB Reactome Pathways, MSigDB GO Biological Process, and MSigDB Immunologic Signatures), and Blood Transcription Modules [15]. Pathway enrichment analysis will be conducted using the goseq algorithm [16] to adjust for RNA-Seq-specific gene length bias¹. Pathways with a FDR-adjusted p-value < 0.05 will be considered significantly enriched. Due to the relatively increased number of pathways in the MSigDB Immunologic Signatures set, a more stringent FDR-adjusted

¹ For RNA-Seq, longer genes tend to obtain higher read counts compared to shorter genes as they occupy a higher proportion of the transcriptome/genome space. As such gene expression based on read counts is not only proportional to the actual expression but a combination of read length and actual expression. This results in greater statistical power for detecting differential genes if they are long and highly expressed. The effect needs to be addressed in gene set enrichment analysis as comparisons are made between sets of genes. Otherwise gene sets that on average contain larger genes will more likely be identified as significantly enriched compared to gene sets with on average smaller genes.

p-value < 0.01 will be used. Pathway enrichment results including gene set annotation, gene set size, number of DE genes in a gene set by up and down-regulation, Jaccard similarity index, p-value, and FDR-adjusted p-value will be listed (Table 130). For enriched KEGG pathways, log₂ fold change from baseline will be overlaid on top of pathway maps and significantly up/and down-regulated genes (DE genes) will be highlighted to facilitate visual interpretation (Figure 12, left panel). Overlap between sets of identified enriched pathways will be summarized using UpSet plots (similar to Figure 10). Gene set enrichment trends across study arms and post-vaccination days will be visualized using heatmaps color-coded by enrichment score ($-1 \times \log_{10}(\text{enrichment p-value})$) (Figure 12, middle panel) as well as time trend plots of median pathway responses (based on median average log₂ fold changes of all pathway members) and associated 95% bootstrap confidence intervals (CIs) (similar to Figure 11, right panel).

9.3.4. Protein-Protein Interactions Network Analysis

To further characterize DE genes, experimentally determined protein-protein interaction networks including known Influenza A-host interactions centered around DE genes will be generated using data from the IntAct database [17]. Networks will be visualized using *Cytoscape* [18] (Figure 12, right panel). This analysis will be performed for DE genes that differed between the H7N9 arms.

10. SAFETY EVALUATIONS

Summaries and analysis of safety data will be presented for the Safety Analysis Population. These include reactogenicity following each study vaccination, unsolicited adverse events, and adverse events of special interest including SAEs/MAAEs, new-onset chronic medical conditions, and potentially immune-mediated medical conditions. The goal of the safety summaries is to provide information to guide the exploratory correlation analysis to identify transcriptomic/proteomic changes that are predictive of certain safety profiles. The exploratory correlation analysis will be described in an addendum to this SAP. The following sections describe planned baseline and safety summaries.

10.1. Demographic and Other Baseline Characteristics

Summaries of age, sex, ethnicity, and race will be presented by study arm and overall for all enrolled subjects (Table 11 and Table 12). Ethnicity will be categorized as Hispanic or Latino, or not Hispanic and not Latino. In accordance with NIH reporting policy, subjects may self-designate as belonging to more than one race or may refuse to identify a race, the latter reflected in the CRF as “No” to each racial option. Individual subject listings will be presented for all demographics (Listing 6); pre-existing medical conditions (Listing 7); and concomitant medications (Listing 15). The number of subjects with pre-existing medical conditions by MedDRA System Organ Class and study arm will be provided as shown in Table 13. Summaries of medications that were started prior to dosing and continuing at the time of dosing will be presented by WHO Drug Level 1 and Level 2 codes and study arm for subjects in the safety population (Table 153). The number of doses of study product administered to subjects will be presented by study arm as part of the subject disposition table (Table 8).

10.2. Adverse Events

10.2.1. Solicited Events and Symptoms

Systemic and upper respiratory (local) solicited adverse events were collected pre-vaccination, and systemic and local solicited adverse events were collected 30 minutes post-vaccination and then daily for 7 days after first vaccination and graded on a scale of 0 (absent), 1 (mild), 2 (moderate) and 3 (severe). The grading scales for solicited systemic and local (administration site) adverse events are provided in Table 3, Table 4, Table 5, and Table 6. The percentage of subjects and associated exact Clopper–Pearson 95% CI reporting at least one solicited adverse event will be summarized for each solicited adverse event, any systemic symptom, any local symptom, and any symptoms (Table 132, Table 133, Table 134). In addition, for each systemic and local event, any systemic event, any local event, and any solicited event, the maximum severity over 7 days after each vaccination will be summarized for the Safety population. For each event the denominator is the number of subjects with non-missing data for the specific event (Table 135, Table 136, Table 137). The number of subjects reporting a solicited adverse event will be summarized for each day post vaccination in a summary table (Table 138, Table 139, Table 140, Table 141, Table 142) and graphically in a bar chart (Figure 13). Solicited adverse events by subject will be presented in Listing 10 and Listing 11.

10.2.2. Unsolicited Adverse Events

When calculating the incidence of unsolicited AEs (i.e., on a per subject basis), each subject will only be counted once at the highest severity and/or relationship, and any repetitions of the same AEs within a subject will be ignored; the denominator will be the total number of subjects in the safety population. The number and percentage and associated 95% CI of subjects reporting at least one unsolicited AE will be summarized by MedDRA system organ class and preferred term (Table 143, Table 144, Table 145). Denominators for

percentages are the number of subjects who received the study vaccination summarized. In addition, a summary of the percentage of subjects by MedDRA system organ class, preferred term, severity, and relationship to study product will be provided (Table 146, Table 147, Table 148). Bar charts of the incidence of non-serious adverse events by severity and MedDRA system organ class will be generated as shown in Figure 14. A listing of all reported AEs by subject sorted by study group, subject ID, and AE Number will be presented as specified in Listing 12.

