6. GENERAL STATISTICAL CONSIDERATIONS

6.1. General Principles

Continuous variables will be summarized using descriptive statistics (n, mean, standard deviation, median, interquartile range (IQR), minimum, and maximum) unless otherwise specified. The frequency and percentages (based on the analysis population size) of observed levels will be reported for all categorical measures. In general, all data will be listed and sorted by study arm and subject, and when appropriate, by study visit number within subject. All summary tables will be structured with a column for each study arm in the following order: Study Arm 1, Study Arm 2, and Study Arm 3.

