14.4.1.2 Solicited Adverse Events

Table 132: Number and Percentage of Subjects Experiencing Solicited Events with 95% Confidence Intervals by Symptom, and Treatment Group (Post-First Vaccination)

	Study Arm 1 A/H3N2v, D1 (N=X)			Study Arm 2 A/H7N9 + AS03, D1, 29 (N=X)			Study Arm 3 A/H7N9 + PBS, D1, 29 (N=X)		
	n	%	95% CI	n	%	95% CI	n	%	95% CI
Any Symptom	x	xx	x x, x.x	x	xx	x x, x x	x	xx	x x, x x
Any Systemic Symptom	x	xx	x x, x.x	x	xx	x x, x x	x	xx	x x, x x
[Systemic Symptom 1]	x	xx	x x, x.x	x	xx	x x, x x	x	xx	x x, x x
[Systemic Symptom 2]	x	xx	x x, x.x	x	xx	x x, x x	x	xx	x x, x x
Any Local Symptom	x	xx	x x, x.x	x	xx	x x, x x	x	xx	x x, x x
[Local Symptom 1]	x	xx	x x, x.x	x	xx	x x, x x	x	xx	x x, x x
[Local Symptom 2]	x	xx	x x, x.x	x	xx	x x, x x	x	xx	x x, x x

N= Number of subjects in the per safety analysis population.

Tables with similar format:

Table 133: Number and Percentage of Subjects Experiencing Solicited Events with 95% Confidence Intervals by Symptom, and Treatment Group (Post-Second Vaccination)

Table 134: Number and Percentage of Subjects Experiencing Solicited Events with 95% Confidence Intervals by Symptom, and Treatment Group (Post-Any Vaccination)

Table 135: Number and Percentage of Subjects Experiencing Solicited Events by Symptom, Maximum Severity, and Treatment Group (Post-First Vaccination)

Symptom	Severity	Study Arm 1 A/H3N2v, D1 (N=X)			Study Arm 2 A/H7N9 + AS03, D1, 29 (N=X)			Study Arm 3 A/H7N9 + PBS, D1, 29 (N=X)		
		n	%	95% CI	n	%	95% CI	n	%	95% CI
Any Symptom	None	x	xx	x x, x.x	x	xx	x.x, x x	x	xx	x x, x.x
	Mild	x	xx	x x, x.x	x	xx	x.x, x x	x	xx	x x, x.x
	Moderate	x	xx	x x, x.x	x	xx	x.x, x x	x	xx	x x, x.x
	Severe	x	xx	x x, x.x	x	xx	x.x, x x	x	xx	x x, x.x
Systemic Symptoms										
Any Systemic Symptom	None	x	xx	x x, x.x	x	xx	x.x, x x	x	xx	x x, x.x
	Mild	x	xx	x x, x.x	x	xx	x.x, x x	x	xx	x x, x.x
	Moderate	x	xx	x x, x.x	x	xx	x.x, x x	x	xx	x x, x.x
	Severe	x	xx	x x, x.x	x	xx	x.x, x x	x	xx	x x, x.x
[Systemic Symptom 1]	None	x	xx	x x, x.x	x	xx	x.x, x x	x	xx	x x, x.x
	Mild	x	xx	x x, x.x	x	xx	x.x, x x	x	xx	x x, x.x
	Moderate	x	xx	x x, x.x	x	xx	x.x, x x	x	xx	x x, x.x
	Severe	x	xx	x x, x.x	x	xx	x.x, x x	x	xx	x x, x.x
[Systemic Symptom 2]	None	x	xx	x x, x.x	x	xx	x.x, x x	x	xx	x x, x.x
	Mild	x	xx	x x, x.x	x	xx	x.x, x x	x	xx	x x, x.x
	Moderate	x	xx	x x, x.x	x	xx	x.x, x x	x	xx	x x, x.x
	Severe	x	xx	x x, x.x	x	xx	x.x, x x	x	xx	x x, x.x
Local Symptoms										
Any Local Symptom	None	x	xx	x x, x.x	x	xx	x.x, x x	x	xx	x x, x.x

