	Mild	x	xx	x x, x.x	x	xx	x.x, x x	x	xx	x x, x.x
	Moderate	x	xx	x x, x.x	x	xx	x.x, x x	x	xx	x x, x.x
	Severe	x	xx	x x, x.x	x	xx	x.x, x x	x	xx	x x, x.x

		Study Arm 1 A/H3N2v, D1 (N=X)			Study Arm 2 A/H7N9 + AS03, D1, 29 (N=X)			Study Arm 3 A/H7N9 + PBS, D1, 29 (N=X)		
[Local Symptom 1]	None	x	xx	x x, x.x	x	xx	x.x, x x	x	xx	x x, x.x
	Mild	x	xx	x x, x.x	x	xx	x.x, x x	x	xx	x x, x.x
	Moderate	x	xx	x x, x.x	x	xx	x.x, x x	x	xx	x x, x.x
	Severe	x	xx	x x, x.x	x	xx	x.x, x x	x	xx	x x, x.x
[Local Symptom 2]	None	x	xx	x x, x.x	x	xx	x.x, x x	x	xx	x x, x.x
	Mild	x	xx	x x, x.x	x	xx	x.x, x x	x	xx	x x, x.x
	Moderate	x	xx	x x, x.x	x	xx	x.x, x x	x	xx	x x, x.x
	Severe	x	xx	x x, x.x	x	xx	x.x, x x	x	xx	x x, x.x
N = Number of subjects in the Safety Analysis Population who received the specified dose. Severity is the maximum severity reported over all solicited symptoms post dosing for each subject.										

Tables with similar format:

Table 136: Number and Percentage of Subjects Experiencing Solicited Events by Symptom, Maximum Severity, and Treatment Group (Post-Second Vaccination)

Table 137: Number and Percentage of Subjects Experiencing Solicited Events by Symptom, Maximum Severity, and Treatment Group (Post-Any Vaccination)

Table 138: Number and Percentage of Subjects Experiencing Solicited Events by Symptom, Severity, and Post-Vaccination Day (Post-First Vaccination, Study Arm 1 A/H3N2v, D1)

Study Arm 1 A/H3N2v, D1 (N=X)																			
Symptom	Severity	Pre-Vaccination 1		Post-Vaccination 1		Day 1		Day 2		Day 3		Day 4		Day 5		Day 6		Day 7+	
		n	%	n	%	n	%	n	%	n	%	n	%	n	%	n	%	n	%
Any Symptom	None	x	xx	x	xx	x	xx	x	xx	x	xx	x	xx	x	xx	x	xx	x	xx
	Mild																		
	Moderate																		
	Severe																		
	Not Reported																		
Systemic Symptoms																			
Any Systemic Symptom	None	x	xx	x	xx	x	xx	x	xx	x	xx	x	xx	x	xx	x	xx	x	xx
	Mild																		
	Moderate																		
	Severe																		
	Not Reported																		
[Systemic Symptom 1]	None																		
	Mild																		
	Moderate																		
	Severe																		
	Not Reported																		
[Systemic Symptom 2]	None																		
	Mild																		

Study Arm 1 A/H3N2v, D1 (N=X)																			
Symptom	Severity	Pre-Vaccination 1		Post-Vaccination 1		Day 1		Day 2		Day 3		Day 4		Day 5		Day 6		Day 7+	
		n	%	n	%	n	%	n	%	n	%	n	%	n	%	n	%	n	%
	Moderate																		
	Severe																		
	Not Reported																		

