14.4.1.3 Unsolicited Adverse Events

Table 143: Number and Percentage of Subjects Experiencing Unsolicited Adverse Events with 95% Confidence Intervals by MedDRA® System Organ Class and Preferred Term, and Treatment Group (Post-First Vaccination)

MedDRA® System Organ Class	MedDRA® Preferred Term	Study Arm 1 A/H3N2v, D1 (N=X)			Study Arm 2 A/H7N9 + AS03, D1, 29 (N=X)			Study Arm 3 A/H7N9 + PBS, D1, 29 (N=X)		
		n	%	95% CI	n	%	95% CI	n	%	95% CI
Any SOC	Any PT	x	xx	xx, xx	x	xx	xx, xx	x	xx	xx, xx
[SOC 1]	Any PT									
	[PT 1]									
	[PT 2]									
[SOC 2]	Any PT									
	[PT 1]									
	[PT 2]									

Note: N = number of subjects in the Safety Analysis Population who received the specified dose.
This table presents number and percentage of subjects. A subject is only counted once per PT.

Tables with similar format:

Table 144: Number and Percentage of Subjects Experiencing Unsolicited Adverse Events with 95% Confidence Intervals by MedDRA® System Organ Class and Preferred Term, and Treatment Group (Post-Second Vaccination)

Table 145: Number and Percentage of Subjects Experiencing Unsolicited Adverse Events with 95% Confidence Intervals by MedDRA® System Organ Class and Preferred Term, and Treatment Group (Post-Any Vaccination)

Table 146: Number and Percentage of Subjects Experiencing Unsolicited Adverse Events by MedDRA® System Organ Class and Preferred Term, Maximum Severity, and Relationship (Study Arm 1 A/H3N2v, D1)

Study Arm 1 A/H3N2v, D1 (N=X)													
MedDRA® System Organ Class	MedDRA® Preferred Term	Any Incidence		Severity [1]						Relationship to Treatment [2]			
				Mild		Moderate		Severe		Not Related		Related	
		n	%	n	%	n	%	n	%	n	%	n	%
Any SOC	Any PT	x	xx	x	xx	x	xx	x	xx	x	xx	x	xx
[SOC 1]	Any PT												
	[PT 1]												
	[PT 2]												
[SOC 2]	Any PT												
	[PT 1]												
	[PT 2]												

Note: N = Number of subjects in the Safety Analysis Population.
 [1] For severity, a subject is counted once per preferred term and is summarized according to their highest severity.
 [2] For relationship, a subject is only counted once per preferred term and is summarized according to their closest relationship.

Tables with similar format:

Table 147: Number and Percentage of Subjects Experiencing Unsolicited Adverse Events by MedDRA® System Organ Class and Preferred Term, Maximum Severity, Relationship (Study Arm 2 A/H7N9 + AS03, D1, 29)

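### SAP Tables 133 and 136 report the same post-dose-2 solicited reactions over different denominators, and SAP 10.2.2 states two denominators for unsolicited events

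*SAP*

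**What the plan says.** **General rule.** SAP 6.1: "The frequency and percentages (based on the analysis population size) of observed levels will be reported for all categorical measures". SAP 6.3.1 puts anyone with at least one dose in the safety population, so it includes A/H7N9 subjects who never received dose 2.

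**Solicited events.**
- Table 132 footnote: "N= Number of subjects in the per safety analysis population". Table 133 (post-second vaccination) and Table 134 (post-any) reuse this shell.
- Table 135 footnote: "N = Number of subjects in the Safety Analysis Population who received the specified dose". Table 136 (post-second) and Table 137 (post-any) reuse this shell.
- SAP 10.2.1, on maximum severity in Tables 135-137: "For each event the denominator is the number of subjects with non-missing data for the specific event".

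**Unsolicited events.**
- SAP 10.2.2, on incidence per subject: "the denominator will be the total number of subjects in the safety population".
- The same paragraph, straight after citing Tables 143-145, says that denominators for "percentages are the number of subjects who received the study vaccination summarized".
- Table 143 footnote, reused for Tables 144 and 145: "N = number of subjects in the Safety Analysis Population who received the specified dose".
- Tables 146-148 are laid out by arm, not by dose, and their footnote gives the safety population.

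**Study Arm 1.** The A/H3N2v arm gets one dose only (SAP Table 1). The shells for Tables 132, 135 and 143, and so for Tables 133, 136 and 144, carry a Study Arm 1 column with no n/a marking.

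**The concern.** Tables 133 and 136 describe the same events: solicited reactions after the second vaccination, by symptom and arm. One gives the percentage with any reaction and an exact interval; the other splits it by severity. A reader expects the severity rows to add up to the overall percentage. Under the footnotes as written they need not, because one N includes subjects who had no second dose and the other does not.

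A subject without dose 2 cannot contribute a post-dose-2 reaction to the numerator, so keeping that subject in the denominator can only lower the percentage. The protocol expects some subjects to miss dose 2. Section 5.2.3 lists reasons for withholding it, including certain Grade 3 events after dose 1 and ongoing Grade 2 or 3 events. Sections 5.2.4 and 6.3 keep these subjects in safety follow-up. The tertiary endpoints for solicited events are defined per vaccination, so a percentage over people not vaccinated does not match the endpoint.

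The Study Arm 1 column raises a separate problem. Filled over the safety population, it reports no reactions to a dose that was never planned.

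**Working it through.** The documents state no figure for this point, so there is none to reproduce. The check has two parts.

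**1. Denominator rules side by side**

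| Summary after dose 2 | Text | Footnote |
|---|---|---|
| Table 133, solicited, any | 6.1: analysis population size | safety population |
| Table 136, solicited, by severity | 10.2.1: non-missing for the event | recipients of the dose |
| Table 144, unsolicited | 10.2.2: both safety population and recipients | recipients of the dose |

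The solicited tables conflict with each other. In the unsolicited block the conflict is confined to the 10.2.2 text: the Table 144 footnote chooses recipients, and the safety-population clause fits only summaries not split by dose.

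**2. Size**

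Inputs: 10 subjects per arm (SAP Table 1); A/H7N9 subjects who miss dose 2 are replaced so that at least 10 evaluable subjects per A/H7N9 arm remain (Protocol 5.2.4); exact Clopper-Pearson 95% intervals (SAP 10.2.1). Assumptions, since no dose-2 drop-out rate is given: k = 1, 2 or 3 subjects without dose 2, and 4 reactors among dose-2 recipients.

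*With replacement.* Recipients = 10, safety N = 10 + k. Relative understatement = 1 − 10/(10 + k) = k/(10 + k).

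| k | Recipients | Safety population | Understatement |
|---|---|---|---|
| 1 | 4/10 = 40.0% | 4/11 = 36.4% | 1/11 = 9% |
| 2 | 4/10 = 40.0% | 4/12 = 33.3% | 2/12 = 17% |
| 3 | 4/10 = 40.0% | 4/13 = 30.8% | 3/13 = 23% |

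The interval for 4/10 is 12.2% to 73.8%.

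*Without replacement.* Recipients = 10 − k, safety N = 10. Relative understatement = k/10, that is 10%, 20% or 30%. For k = 2: 4/8 = 50.0% (15.7% to 84.3%) against 4/10 = 40.0%.

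*All three solicited rules at once.* With replacement, k = 2, and one non-reacting recipient with missing data: 4/12 = 33.3%, 4/10 = 40.0%, 4/9 = 44.4%.

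*Study Arm 1 after dose 2.* Safety population: 0/10 = 0%, upper limit 1 − 0.025^(1/10) = 30.8%. Recipients: 0/0, undefined.

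*Chance that it matters in one arm.* P(at least one of 10 misses dose 2) = 1 − (1 − p)^10. For assumed p of 2%, 5%, 10% and 20% this is 18%, 40%, 65% and 89%.

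**The case against.** The case against giving this weight is fair in several respects.

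- **Unsolicited tables.** A reader of 10.2.2 might infer that unsolicited tables will show the same events with different percentages. The shells do not support that. Table 144 uses dose recipients, and Tables 146-148 pool both doses, so they are not the same summary. What stands is an ambiguous paragraph.
- **AS03 arm.** A reader might infer that the dilution necessarily falls hardest on the AS03 arm. Protocol 2.3.1 does say solicited reactions are more frequent with AS03, and some withholding reasons are reactions to dose 1. But other listed reasons are refusal, noncompliance and loss to follow-up, and no withholding rate by arm is given. A larger effect there is possible, not shown.
- **Footnotes and header N.** The Table 132 footnote looks garbled, and a header N can coexist with a per-event denominator. That may well explain the text, but nothing restricts Table 133 to dose recipients, and 6.1 points to the full population.
- **Study Arm 1.** The false 0% cannot arise in Tables 136 or 144, where the footnotes give that arm N = 0. Only Table 133 is exposed. Elsewhere the SAP prints n/a for this arm after dose 2 (Tables 14, 26, 74, 122 and 126), and the daily post-second tables (141-142) exist only for Arms 2 and 3. This suggests an oversight.
- **Informative withholding.** Using recipients does not cure it: subjects who reacted badly to dose 1 still drop out of the dose-2 summary. That is true. The change makes the percentage describe those dosed and makes the tables agree; it does no more.
- **Consequence.** Safety is tertiary, the study is hypothesis-generating (Protocol 11.2), and Listings 1 and 10-12 allow recalculation by subject.

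**Conclusion.** The point holds for the dose-2 solicited tables and, as an ambiguity of text, for 10.2.2. Followed as written, Table 133 gives a lower percentage than Table 136 for the same reactions whenever an A/H7N9 subject misses dose 2. The replacement scenario is the one to use, because Protocol 5.2.4 says these subjects will be replaced; the larger no-replacement figures apply only if replacement fails. Both rest on an assumed number of undosed subjects. If nobody misses dose 2 and no event data are missing, all rules agree in Arms 2 and 3, and only the Study Arm 1 column of Table 133 remains wrong.

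A reader might also conclude that one dose-recipient rule should govern every table from 132 to 148. The layouts do not support that: the post-any tables and Tables 146-148 are not dose-specific, and the daily tables already account for missing reports with Not Reported rows.

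Severity is minor. No between-arm safety test is planned, and no sample size or primary endpoint is affected.

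**What to change.** 1. **Post-first and post-second tables (132-133, 135-136, 143-144):** use recipients of the dose summarised and, for solicited events, those with at least one post-dose assessment of that event. Correct the Table 132/133 footnote and align 10.2.1 with it.
2. **Post-any tables (134, 137, 145) and Tables 146-148:** keep the safety population. Limit the clause "the denominator will be the total number of subjects in the safety population" in 10.2.2 to these tables.
3. **Daily Tables 138-142:** leave dose recipients as N, with the existing Not Reported rows.
4. **Study Arm 1:** print n/a in Tables 133, 136 and 144.

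The cost is a few sentences in 10.2.1 and 10.2.2, some footnotes and three table columns. No new data or analyses are needed.
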